CSF samples will be collected for the determination of CSF E2027 concentrations at Week 9. At this visit, a predose blood sample for PK will be taken first, followed by CSF sampling. Study drug will then be administered to the subjects. Another PK sample will be collected at 1 to 4 hours postdose.

Baseline Biomarker Assessments

A plasma sample will be collected during the Screening Period (Tier 3) to measure biomarkers related to Alzheimer’s disease (AD) copathology (including amyloid and p-tau) and other biomarkers related to DLB or PDD. These baseline plasma amyloid A β 42/A β 40 ratio will be used to classify subjects into the various categories (DLB without amyloid copathology, DLB with amyloid copathology, PDD without amyloid copathology and PDD with amyloid copathology). The baseline plasma and CSF biomarkers may also be used to define other subgroups classifications of subjects for subgroup analyses.

A CSF sample will be collected during the Screening Period (at least 7 days before the Baseline Visit) to measure baseline CSF cGMP and biomarkers related to DLB or PDD. These DLB or PDD related biomarkers may be used to define other subgroups classifications of subjects for subgroup analyses.

Pharmacodynamic Assessments

CSF samples will be collected during the Screening Period (at least 7 days before the Baseline Visit) and after 9 weeks on E2027. Both samples should be collected at approximately the same time in the morning, either in the fasted state (preferred) or at least 2 hours after breakfast. The CSF sample during the Treatment Period should be collected after the predose blood draw for PK and plasma biomarker analysis at the study visit after 9 weeks on E2027. The CSF samples will be assayed for cGMP and E2027. Other CSF biomarkers related to DLB or PDD or E2027 PD effects may also be assayed, if appropriate.

A predose plasma sample will be collected at the study visit after 9 weeks on E2027. It will be assayed for plasma biomarkers related to DLB or PDD or E2027 PD effects on these biomarkers if appropriate.

Pharmacogenomic Assessments

Blood samples will be collected as specified in the Schedule of Procedures/Assessments where feasible and in accordance with local regulations. Participation in pharmacogenomic (PGx) assessments is voluntary and subjects must provide a separate informed consent before blood collection for PGx assessments.

The PGx blood samples may be used to genotype common and rare genetic variants (including apolipoprotein E [ApoE] genotype). Data obtained from the PGx analysis will be used for research, to assist in developing safer and more effective treatments and will not be used to change the diagnosis of the subject or alter the therapy of the subject. The deoxyribonucleic acid (DNA) will not be used to determine or predict risks for diseases that an individual subject does not currently have. Any sample may be stored for up to 15 years, based on country specific regulations to assist in any scientific research questions related to E2027 or DLB or PDD.

Safety Assessments

Safety will be assessed by monitoring and recording all AEs, regular monitoring of hematology, blood chemistry and urinalysis, measurement of vital signs (including orthostatic changes), ECGs, and the performance of physical examinations, C-SSRS, and UPDRS-III. A safety brain MRI may also be performed at Unscheduled Visits if deemed appropriate by the investigator.

C-SSRS

An assessment of suicidality using the C-SSRS will be performed at Screening and Baseline Visits, every 3 weeks during the Treatment Period, and at the Follow-Up Visit.

MDS UPDRS-III: Motor Examination

This scale evaluates extrapyramidal features in motor function in Parkinson's disease. It contains 33 items in 18 categories: (1) speech, (2) facial expression, (3) rigidity, (4) finger tapping, (5) hand movements, (6) supinational and pronation movements of hands, (7) toe tapping, (8) leg agility, (9) arising from chair, (10) gait, (11) freezing of gait, (12) postural stability, (13) posture, (14) body bradykinesia, (15) postural tremor of hands, (16) kinetic tremor of hands, (17) rest tremor amplitude and (18) constancy of rest tremor. Each item is scored 0 to 4, giving a total score range 0 to 132. It is recommended that the motor assessments should be made with the subject in the "on" state at each visit and at the same time relative to the subject's last dose of Parkinson's disease medication (such as L-dopa).

Bioanalytical Methods

Plasma concentrations of E2027 and its metabolite HP4 and CSF concentrations of E2027 will be measured using a validated liquid chromatography tandem mass spectrometry (LC-MS/MS) assay methods.

Plasma concentrations of A β 42 and A β 40 will be measured by the validated immunoprecipitation LC-MS/MS C2N Preclivity plasma assay. Plasma concentrations of p-tau 181, glial fibrillary acidic protein (GFAP), and neurofilament light (NFL) will be measured by Quanterix Simoa plasma assay.

CSF concentrations of cGMP will be measured using a validated assay. Other CSF biomarkers represented by A β 42, A β 40, tau, p-tau will be measured by Lumipulse platform and CSF NFL, neuregulin (NRG) will be measured by Simoa.

Statistical Methods

Primary Endpoint

- Percentage change from baseline in CSF cGMP at 9 weeks of treatment.

Secondary Endpoints

- Safety and tolerability of E2027 as measured by the following:
 - Incidence of AEs including severe AEs, serious AEs, AEs resulting in discontinuation
 - Incidence of orthostatic hypotension and orthostatic tachycardia
 - Incidence of markedly abnormal laboratory values and shifts from baseline of laboratory values

- Incidence of abnormal ECG parameters and abnormal ECG findings
- Incidence of suicidality based on C-SSRS
- Changes from baseline in the total score of UPDRS-III

Exploratory Endpoints

- The following clinical efficacy endpoints at 12 weeks of treatment
 - Change from baseline in MoCA total score
 - Change from baseline in WAIS-IV DSC score
 - CIBIC-Plus scale
 - CGIC scale
 - Change from baseline in CFI score
 - Change from baseline in MMSE total score
 - Change from baseline in NPI total score, subscores and caregiver distress score
 - Change from baseline in SAPS-PD total score
 - Change from baseline in FAQ total score
- Change from baseline in CSF cGMP at 9 weeks of treatment
- Percentage change and change from baseline at 9 weeks of treatment in other biomarkers in CSF and/or plasma, including using other diagnostic subgroups classifications based on baseline biomarkers (if appropriate)
- PK of E2027 in subjects with DLB or PDD, using population modelling
- Relationships between E2027 in plasma/CSF and its effects on the following variables using PK/PD modelling, if data permit:
 - Plasma/CSF PD biomarkers (including CSF cGMP),
 - Clinical efficacy (including MoCA, WAIS-IV DSC, CIBIC-Plus, NPI, MMSE, CFI, SAPS-PD, FAQ, and CGIC at 12 weeks of treatment),
 - Safety variables
- Relationships of the plasma and CSF PD biomarkers compared to MoCA, WAIS-IV DSC, CIBIC-Plus, NPI, MMSE, CFI, SAPS-PD, FAQ, and CGIC at 12 weeks of treatment, if data permit
- Relationships amongst plasma biomarkers and CSF biomarkers at baseline and after treatment (if appropriate)
- Subgroup analyses based on genotype classification for CSF cGMP changes from baseline and clinical endpoints

Analysis Sets

- The Safety Analysis Set is the group of subjects who receive at least 1 dose of study drug and have at least 1 post baseline safety assessment
- The Full Analysis Set (FAS) is the group of subjects who receive at least 1 dose of study drug and have baseline and at least 1 post baseline MoCA measurement
- The PD Analysis Set is the group of subjects who have sufficient PD data to derive at least 1 PD parameter

Efficacy Analyses

The exploratory efficacy endpoints will be summarized based on the FAS, by subject subgroup (DLB without amyloid copathology, DLB with amyloid copathology, PDD without amyloid copathology, and PDD with amyloid copathology).

Pharmacokinetic, Pharmacodynamic and Pharmacogenomic Analyses**Pharmacokinetic Analyses**

The Safety Analysis Set will be used for E2027 concentration listings and for summaries of E2027 concentrations in plasma and CSF by dose and day.

A population PK approach will be used to characterize the plasma PK of E2027. For this approach, PK data from this study will be pooled with relevant data from Phase 1 and 2 studies. As appropriate, the effect of covariates on the PK of E2027, such as baseline characteristics/demographics will be evaluated. Derived exposure parameters such as steady state area under the concentration time curve or average concentration of E2027 and other derived parameters may be calculated from the final PK model using the individual posterior estimates of the PK parameters and dosing history. The details will be described in the separately prepared analysis plan and its report, and the results will not be included in the clinical study report.

Pharmacodynamic Analyses

The PD Analysis Set will be used for the summaries and analyses of CSF and plasma PD biomarkers. The percentage change from baseline in CSF cGMP at 9 weeks of treatment will be analyzed to compare different subject subgroups (DLB without amyloid copathology vs DLB with amyloid copathology, and PDD without amyloid copathology vs PDD with amyloid copathology). Analyses, comparing the different subgroups, of the percentage change from baseline in CSF cGMP will be performed using an analysis of covariance, where baseline CSF cGMP will be included as a covariate. The least square (LS) means, LS mean subgroup differences and 95% CIs will be presented.

The change from baseline in CSF cGMP at 9 weeks of treatment will also be analyzed. Other CSF and plasma PD biomarkers may be analyzed similarly, if appropriate.

The CSF and plasma PD biomarkers will be summarized by subject subgroups, as appropriate. Summaries and figures will be produced exploring the relationships between CSF and plasma PD biomarkers and the efficacy endpoints.

Pharmacodynamic/Pharmacokinetic Analyses

The correlation amongst plasma and CSF exposure to E2027 and the various efficacy and biomarker endpoints will be explored graphically. The details will be described in the separately prepared analysis plan and its report, and the results will not be included in the clinical study report.

Pharmacogenomic Analyses

The percentage change in CSF cGMP at 9 weeks, change in CSF cGMP at 9 weeks and other CSF and plasma PD biomarkers will be summarized by ApoE4 status, using the PD Analysis Set. Other PGx data will be summarized similarly.

Safety Analyses

Evaluations of safety will be performed on the Safety Analysis Set. The incidence of AEs, out-of-normal-range laboratory safety test variables, abnormal ECG findings, and out-of-range vital signs, suicidality (C-SSRS), UPDRS-III, along with change from baseline in laboratory safety test variables, ECGs, and vital sign measurements (including orthostatic changes) will be summarized by subgroup and overall.

Interim Analyses

No interim analysis will be conducted.

Sample Size Rationale

Assuming the standard deviation of percentage change from baseline in CSF cGMP at Week 9 is 60, the sample size of 6 completers per group (for 8 enrolled subjects per arm, assuming a 25% dropout rate), will have approximately 80% power to detect the difference in change from baseline of CSF cGMP of 100% between the DLB without amyloid copathology subgroup and the DLB with amyloid copathology subgroup. The analysis between the PDD without amyloid copathology subgroup and the PDD with amyloid copathology subgroup, also has approximately 80% power to detect the difference in change from baseline of CSF cGMP of 100% (same assumptions as above). These sample size calculations illustrate the possible differences that could be seen between subgroups. However, without previous data on the differences between subgroups in CSF cGMP, these are for illustration only and it is not expected statistical significance will be reached with 6 subjects per subgroup.

The probability of observing a difference in percentage of CSF cGMP between 2 subgroups (DLB without amyloid copathology subgroup minus DLB with amyloid copathology subgroup, or PDD without amyloid copathology subgroup minus PDD with amyloid copathology subgroup) $\geq 30\%$ depends on the true difference between the 2 groups. If the true difference is 100%, there will be 97.8% probability that the observed difference is $\geq 30\%$. If the true difference is 60%, the probability is 80.7%. If the true difference is 10%, there will be 28.2% probability that the observed difference is $\geq 30\%$.

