At the Baseline Visit subjects will be assessed regarding other medical conditions and concomitant medications (including medications for DLB or PDD) to ensure that these remain stable with no changes to treatment required and that they do not interfere with their safety or study procedures. Other safety assessments including vital signs, ECGs, laboratory tests, and Columbia Suicide Severity Rating Scale (C-SSRS) will also be conducted.

Treatment Phase

Treatment Period: After completing study assessments at the Baseline Visit, subjects who continue to be eligible will proceed to the Treatment Period on E2027 (50 mg once daily [QD]). They will be provided with E2027 to start administration in the morning of Day 1 at home. They will continue to take study drug for 12 weeks. During the Treatment Period study visits will be conducted after 3, 6, 9, and 12 weeks on E2027. Efficacy assessments will be performed after 6 and 12 weeks on E2027 and should be performed at approximately the same time of the day as at the Baseline Visit whenever possible (preferably in the morning). The MoCA should be the first efficacy assessment to be administered, followed by the WAIS-IV DSC (after 12 weeks only), then the CIBIC-Plus and finally the MMSE (after 12 weeks only). Whenever possible, a subject should have the same rater administering the MoCA and the CIBIC-Plus throughout his/her participation in the study. The rater administering the CIBIC-Plus should be independent of the rater(s) who administer the other clinical scales. The caregiver or informant will also complete the CIBIC-Plus, NPI, CFI, SAPS-PD (after 12 weeks only) and FAQ (after 12 weeks only). Safety assessments will be conducted at these visits, including review of adverse events (AEs), vital signs, ECG, laboratory safety tests, C-SSRS, and UPDRS-III. The investigator will review all the efficacy endpoints and safety data at the visits after 6 and 12 weeks on study drug and formulate the CGIC of the subject's clinical status from baseline.

After subjects have completed 9 weeks of treatment with E2027 will have a 2nd CSF sample collected. The CSF sample will be collected in the morning at approximately the same time as at Screening, either in the fasted state or at least 2 hours after breakfast. A 2nd plasma sample for biomarkers will also be collected.

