 - c. DLB subjects who have 2 or more core clinical features by the investigator and the central reviewer and who do not have previous reports of DAT brain imaging scan, MIBG scan or PSG may undertake DAT brain imaging scan or MIBG scan after discussion with the

sponsor medical monitor if the investigator considers that imaging is necessary to confirm the diagnosis.
 
d. PDD subjects with clinical features that are consistent with the diagnostic criteria of probable PDD but in whom the investigator considers that there may be other diagnoses, DAT brain imaging scan or MIBG scan may be conducted after discussion with the sponsor medical monitor.
 
3. MMSE ≥ 14 and ≤ 26 at Screening Visit
 
4. For DLB subjects, have experienced visual hallucinations since onset of their DLB
 
5. If receiving AChEIs, must have been on a stable dose for at least 12 weeks before Screening Visit, with no plans for dose adjustment during the study. Treatment-naïve subjects can be entered into the study but there should be no plans to initiate treatment with AChEIs from Screening to the end of the study.
 
6. If receiving memantine, must have been on a stable dose for at least 12 weeks before Screening Visit, with no plans for dose adjustment during the study. Treatment naïve subjects can be entered into the study but there should be no plans to initiate treatment with memantine from Screening to the end of the study.
 
7. If receiving Parkinson's disease medications, must have been on a stable dose for at least 4 weeks before Screening Visit, with no plans for dose adjustment during the study.
 
8. Must have an identified caregiver or informant who is willing and able to provide follow-up information on the subject throughout the course of the study. This person must, in the opinion of the investigator, not be suffering from cognitive impairment, be sufficiently familiar with the subject and spend sufficient time with the subject on a regular basis such that the caregiver or informant can reliably fulfill the study requirements and must provide separate written consent. The caregiver or informant should normally be residing with the subject. If the caregiver or informant is not residing with the subject, the investigator has to be satisfied that the subject can contact the caregiver or informant readily during the times when the caregiver or informant is not with the subject. As a guide the caregiver or informant should have contact with the subject on at least 4 days a week and each day for a total of at least 5 hours. If in doubt about whether a subject's care arrangements are suitable for inclusion, the investigator should discuss this with the medical monitor. At all visits caregivers or informants need to attend the visit in person along with the subject.
 
9. Provide written informed consent. If a subject lacks capacity to consent in the investigator's opinion, the subject's assent should be obtained, as required in accordance with local laws, regulations and customs, plus the written informed consent of a legal representative should be obtained (capacity to consent and definition of legal representative should be determined in accordance with applicable local laws and regulations). In countries where local laws, regulations, and customs do not permit subjects who lack capacity to consent to participate in this study, they will not be enrolled.

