- In Tier 2, clinical assessments on cognition and depression will be conducted in the morning (whenever possible) in subjects in the following order: MMSE then Geriatric Depression Scale (GDS) should be done first, followed by the MoCA. The caregivers or informants will also complete the Short Fluctuation Questionnaire (SFQ), CFI, and NPI. If the eligibility criteria regarding the MMSE and GDS are not met, the other assessments (SFQ, CFI, and NPI) do not have to be performed and the subject should be screen failed.

- In Tier 3, subjects will be assessed with the Modified Hachinski Ischemic Scale, UPDRS-III, HYS, and C-SSRS. A plasma sample will be collected to measure biomarkers related to AD copathology (amyloid, phosphorylated-tau [p-tau]) and other biomarkers related to DLB or PDD. If a sufficient number of subjects in a subgroup has been achieved, a new subject in that subgroup will be screen failed at Tier 3 or at subsequent tiers. While waiting for the result of the subject's plasma A β 42/A β 40 ratio, the subject may proceed with subsequent tiers.
- In Tier 4, subjects will undertake physical examination, vital signs, ECG, and clinical laboratory tests.
- In Tier 5, subjects will be assessed by safety MRI for brain abnormalities that may affect eligibility.
- In Tier 6, if indicated as judged by the investigator, individual subjects may also undertake DAT brain imaging scan or myocardial MIBG scan to help establish their diagnosis.

It is recommended that where appropriate Tiers 1 to 4 should be performed on the same day and Tiers 5 and 6 on a separate day. However, the investigator may perform the various tiers on separate days as appropriate for each subject. The scores of various clinical scales (including NPI, SFQ, CFI, and UPDRS-III) and cognitive tests (MMSE, MoCA) at Screening will be reviewed by a central process. Subjects who are diagnosed by the investigator with DLB or PDD but whose scores on clinical scales or cognitive tests are found not to be consistent with the diagnosis during central review will be discussed with the investigator to determine their eligibility.

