9.1.1.2 Baseline Period

The Baseline Visit may take place at any time up to 7 days before the first dose of study drug (Day 1, ie, during Day -7 to Day -1, but should take place at least 2 weeks after the Screening Visit Tier 2 assessments) and at least 1 week after CSF collection. Study assessments should be conducted in the morning (whenever possible). Cognition will be assessed by the MoCA,

which must be the first clinical scale to be administered before any invasive procedures, followed by the WAIS-IV DSC and then the Clinician Interview Based Impression of Severity Plus Caregiver Input (CIBIS-Plus). The caregiver or informant will also complete the CIBIS Plus, NPI, CFI, SAPS-PD, and FAQ. The rater administering the CIBIS-Plus should be independent of the rater(s) who administer the other clinical scales.

At the Baseline Visit subjects will be assessed regarding other medical conditions and concomitant medications (including medications for DLB or PDD) to ensure that these remain stable with no changes to treatment required and that they do not interfere with their safety or study procedures. Other safety assessments including vital signs, ECGs, laboratory tests, and C-SSRS will also be conducted.

Subjects who complete the Baseline Period and meet the criteria for inclusion/exclusion (Sections 9.3.1 and 9.3.2) will begin the Treatment Phase.

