e: Unscheduled visits may be conducted at any time as clinically indicated in the judgment of the investigator or as specified in the protocol. Not all assessments indicated under Unscheduled Visits need to be conducted – actual assessments needed will be determined by the investigator or as specified in the protocol and will be based on the specific visit.

f: Tier 2 screening assessments in subjects should be performed in the following order: MMSE and GDS first; then MoCA. The caregivers or informants should complete the SFQ, CFI, and NPI. Subjects who do not meet eligibility criteria on MMSE and GDS should be screen failed and the other assessments do not need to be performed. The above assessments should be completed before more invasive procedures (eg, physical examination, ECG, blood draws). Assessments at all other tiers are not required to be performed in any prespecified order. The caregiver or informant must normally attend in person with the subject. However, under extenuating circumstances only, and only with the approval of the sponsor (eg, during the COVID-19 pandemic), the assessments may be administered remotely via telephone, sponsor-approved telehealth, or home visit.

g: Visit 2, 5, 7, ED Visit and FU study assessments should be conducted at approximately the same time of the day whenever possible (preferably in the morning). The MoCA should be administered first, followed by the WAIS-IV DSC (not at Visit 5), then the CIBIS/CIBIC-Plus and finally the MMSE (not at Visit 5). The caregiver or informant will also complete the CIBIS/CIBIC-Plus, NPI, CFI, SAPS-PD (not at Visit 5) and FAQ (not at Visit 5). The caregiver or informant must normally attend in person with the subject. The CIBIS-Plus and CIBIC-Plus should be performed by an independent rater from other scales. Efficacy assessments should be completed before more invasive

Table 5 Schedule of Procedures/Assessments in Study E2027-A001-203

Phase	Pretreatment		Treatment						
Period	Screening	Baseline	Treatment				Follow-Up (FU)	Early Discontinuation (ED) ^d	Unscheduled ^e
Visit ^a	1 ^b	2 ^c	3 ^c Telephone	4	5	6	7		
Day	-49 to -8	-7 to -1	1	21	42	63	84	112	
Weeks Elapsed Since Start of Treatment			0	3	6	9	12	16	
Assessments									

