9.7.1.1.3 EXPLORATORY ENDPOINTS

- The following clinical efficacy endpoints at 12 weeks of treatment
 - Change from baseline in MoCA total score
 - Change from baseline in WAIS-IV DSC score
 - CIBIC-Plus scale
 - CGIC scale
 - Change from baseline in CFI score
 - Change from baseline in MMSE total score
 - Change from baseline in NPI total score, subscores and caregiver distress score
 - Change from baseline in SAPS-PD total score
 - Change from baseline in FAQ total score
- Change from baseline in CSF cGMP at 9 weeks of treatment

- Percentage change and change from baseline at 9 weeks of treatment in other biomarkers in CSF and/or plasma, including using other diagnostic subgroups classifications based on baseline biomarkers (if appropriate)
- PK of E2027 in subjects with DLB or PDD, using population modelling
- Relationships between E2027 in plasma/CSF and its effects on the following variables using PK/PD modelling, if data permit:
 - Plasma/CSF PD biomarkers (including CSF cGMP),
 - Clinical efficacy (including MoCA, WAIS-IV DSC, CIBIC-Plus, NPI, MMSE, CFI, SAPS-PD, FAQ, and CGIC at 12 weeks of treatment),
 - Safety variables
- Relationships of the plasma and CSF PD biomarkers compared to MoCA, WAIS-IV DSC, CIBIC-Plus, NPI, MMSE, CFI, SAPS-PD, FAQ, and CGIC at 12 weeks of treatment, if data permit
- Relationships amongst plasma biomarkers and CSF biomarkers at baseline and after treatment (if appropriate)
- Subgroup analyses based on genotype classification for CSF cGMP changes from baseline and clinical endpoints

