8 DEFINITIONS AND CONVENTIONS FOR DATA HANDLING

8.1 Efficacy data handling

8.1.1 Pretreatment/Baseline Efficacy

Baseline for all efficacy endpoints is defined as the last pretreatment assessment.

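### MMSE change from baseline runs from the Screening eligibility score, given first and at least 15 days before dosing, to a Week 12 score given last, so the within-subgroup change is not like for like

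*Protocol*

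**What the plan says.** Protocol 9.7.1.1.3 lists "Change from baseline in MMSE total score" at 12 weeks among the exploratory endpoints. SAP 8.1.1 gives one rule for every scale: "Baseline for all efficacy endpoints is defined as the last pretreatment assessment".

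Before treatment, the text places the MMSE only in Screening Tier 2 (Protocol 9.1.1.1), where the order is "MMSE then Geriatric Depression Scale (GDS) should be done first, followed by the MoCA". The same score decides entry: "MMSE ≥ 14 and ≤ 26 at Screening Visit" (Synopsis, Inclusion Criterion 3).

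The Baseline Visit (Protocol 9.1.1.2) starts with the MoCA, "followed by the WAIS-IV DSC and then the Clinician Interview Based Impression of Severity Plus Caregiver Input (CIBIS-Plus"), plus caregiver scales. No MMSE is listed there, in the Synopsis or in 9.5.1.2. In Table 5 the MMSE row has one pretreatment mark, at Screening, while the MoCA, CFI and NPI rows have marks at both Screening and Baseline.

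At Week 12 the MoCA is first, "followed by the WAIS-IV DSC (after 12 weeks only), then the CIBIC-Plus and finally the MMSE (after 12 weeks only").

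Table 5 footnote g points the other way. It covers Visits 2, 5 and 7, the ED Visit and follow-up, and ends the sequence with "then the CIBIS/CIBIC-Plus and finally the MMSE (not at Visit 5"). Exempting only Visit 5 implies an MMSE at Visit 2.

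UPDRS-III is measured at Screening Tier 3 and is absent from the Baseline Visit safety list in 9.1.1.2. It carries a secondary endpoint: "Changes from baseline in the total score of UPDRS-III".

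**The concern.** A change score in a single-arm study carries the drug effect plus everything else that differs between its two ends. For the MMSE three things differ.

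- **Time.** The first score precedes dosing by weeks.
- **Order.** The first score comes from a fresh subject. The last follows three other instruments, one of which, the MoCA, also tests orientation, naming, recall and repetition (SAP 8.4). Fatigue could lower the last score and carry-over could raise it.
- **Selection.** The first score is the one used to admit the subject, so retest values tend to drift towards the mean of the source population. Protocol 9.1.1.1 permits rescreening after a Tier 2 failure because cognition in these diseases varies, and that variation is what produces the drift.

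Protocol 7.3 says it will look for improvement in subjects without amyloid copathology, and for no change or worsening in those with it. Protocol 9.2 includes the MMSE among the scales meant to corroborate Study 201. The direction of MMSE change within a subgroup could therefore be read as evidence when part of it is not an effect of E2027.

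The footnote adds a conduct problem. If some sites give a Visit 2 MMSE and others do not, the SAP rule takes Visit 2 scores for some subjects and Screening scores for others, in subgroups planned at 8 treated and 6 completing.

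**Working it through.** The plan gives no figure of its own to reproduce here. The check is day arithmetic plus a sensitivity calculation on assumed inputs.

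**Age of the baseline.** Inputs: Screening opens on Day -49; the Baseline Visit falls on Day -7 to Day -1; Tier 2 is at least 14 days before it (Protocol 9.1.1.1 and 9.1.1.2); Week 12 is Day 84 (Table 5). There is no Day 0, so Day -k is k days before Day 1, and Day 84 is 83 days after Day 1.

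- Latest MMSE baseline: 1 + 14 = 15 days before Day 1.
- Earliest under the standard windows: 49 days before Day 1.
- Earliest with the 10-week Screening extension (Protocol 9.1.3): 70 + 7 = 77 days.

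Off-drug share = days before Day 1 / (days before Day 1 + 83):

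| Case | Off-drug days | Interval (days) | Share |
|---|---|---|---|
| MMSE, latest Tier 2 | 15 | 98 | 15% |
| MMSE, earliest Tier 2 | 49 | 132 | 37% |
| MMSE, 10-week extension | 77 | 160 | 48% |
| MoCA, for comparison | 1 to 7 | 84 to 90 | 1% to 8% |

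SAP Table 3 starts its Screening window at Day -42, but its footnote a still takes the last pretreatment value, so an earlier MMSE remains the baseline.

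**Regression to the mean.** With a normal source score X of mean m and SD s, and retest correlation r, the expected shift with no drug effect is

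shift = (1 - r) × (m - E[X | 13.5 < X < 26.5]).

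The limits are the inclusive 14 to 26 window with a half-point margin. Protocol 9.3.1 prints strict inequalities; I used the Synopsis form, which matches the 14-19 and 20-26 groups in SAP 5.2.4. The documents give none of m, s or r. I assumed s of 4 to 5 and r of 0.7 to 0.9.

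| Assumed m | Shift in MMSE points over s and r |
|---|---|
| 18 | -0.08 to -0.33 |
| 20 | 0 |
| 22 | +0.08 to +0.33 |
| 24 | +0.17 to +0.69 |

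Worked case: m = 22, s = 5, r = 0.8. The mean inside the window is 20.885, so the shift is 0.2 × (22 - 20.885) = +0.22. The sign depends on whether the source mean lies above or below 20, the centre of the window.

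**Order.** The MMSE is first at Screening and last at Week 12, after the MoCA, WAIS-IV DSC and CIBIC-Plus. No document gives data to size or sign this effect.

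**The case against.** The strongest reply is that little rests on this scale. MMSE is one of nine exploratory scales, and SAP 5.8 plans no formal test. Protocol 9.2 makes the comparison between amyloid subgroups the main one, and a shift common to both cancels there. The within-subgroup correlations in SAP 5.5.2 do not change when a constant is added to every subject. The reasoning behind the 30% cGMP threshold in 9.2 names the MoCA and CIBIC-Plus, and the MoCA has its own Baseline Visit score and the same first position throughout. Giving the MMSE last protects the MoCA. All of this stands. It limits the point to the improved-or-worsened reading within a subgroup, but does not remove it.

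A reader might infer more, and the documents do not support it:

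- **A known upward bias, with order adding to it.** An upward shift requires an assumed source mean above 20, and fatigue and carry-over oppose each other.
- **A bias as large as the drug effect.** The overall Study 201 MoCA difference of 0.181 (95% CI -0.716 to 1.078) is a between-arm result on another instrument, so it is no yardstick for an MMSE shift.
- **Off-drug decline that mimics the amyloid hypothesis.** Protocol 7.3 cites faster brain atrophy with amyloid copathology, but neither document gives an MMSE drift over weeks. A share of days is not a bias in points.
- **The same three faults in UPDRS-III.** Motor eligibility uses Hoehn and Yahr stage, not a UPDRS-III cutoff, and no change of order is shown. Only the timing carries over.

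**Conclusion.** The point holds for the within-subgroup MMSE change. Its baseline is the Screening eligibility score, taken first and 15 to 49 days before Day 1 (up to about 77 with sponsor-approved extension), and its endpoint is a score taken last. Between 15% and 37% of the interval is off drug under the standard windows; the 48% case needs extenuating circumstances and subject-by-subject approval.

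The net direction and size of the bias are unknown. Regression to the mean of about -0.3 to +0.7 points rests entirely on the assumed mean, SD and retest correlation, and the order effect cannot be signed. The contrast between subgroups and the within-subgroup correlations are largely unaffected by a common shift, and the primary cGMP analysis is not affected at all.

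The conflict between footnote g and the rest of the protocol is a plain inconsistency and needs correcting whatever the size of the bias.

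**What to change.** Reconcile Table 5 footnote g, the Table 5 MMSE row, the Synopsis, and Protocol 9.1.1.2 and 9.5.1.2 so that the MMSE is given at the Baseline Visit, last in the battery as at Week 12. SAP 8.1.1 then selects that score without amendment. Keep the Screening MMSE for eligibility. The cost is a few minutes of subject time at an existing visit, and one more practice exposure, possibly only two weeks after Tier 2.

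If the visit is not changed, correct footnote g, title the MMSE outputs as change from Screening, and state in the SAP that the direction of MMSE change will not count as evidence for the pattern in Protocol 7.3. The SAP already describes enrolment and treatment in the past tense, so this may be the only route left. It costs a footnote edit and some table titles.

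For UPDRS-III, either take it at the Baseline Visit, which adds a motor examination there, or label its change as from Screening.
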